4 STUDY VARIABLES

4.1 Baseline Variables

4.1.1 *Demographics and Baseline Characteristics*

- Age at Baseline (Date of Baseline visit - Date of birth)
- Gender (Male/Female)
- Ethnical background (American Indian/Alaska Native, Asian (East Asia), Black, Hawaiian/Pacific Islander, White (Caucasian))
- Site
- Country
- Use of nicotine/Smoking habits (No, Smoking - Less than 10 cigarettes/day, Smoking - Between 11 and 20 cigarettes/day, Smoking - Between 21 and 40 cigarettes/day, Smoking - More than 40 cigarettes/day)
- Snuff (Yes/No) and number of cans per month (for Swedish patients only)

STATISTISKA KONSULTGRUPPEN		Statistical Analysis Plan	
Protocol: Clinical and health economic evaluation with a new Baha abutment design combined with a minimally invasive surgical technique		Protocol No: CBAS5439	
		Version: 1.0	Page 10 of 23

- Type of hearing loss (conductive or mixed hearing loss or single-sided sensorineural deafness)

4.1.2 Medical and Surgical History

Relevant medical and surgical history as judged by the investigator will be coded according to the Medical Dictionary for Regulatory Activities (MedDRA).

4.1.3 Prior and Concomitant Medications

Prior and concomitant medication will be coded according to the Anatomic Therapeutic Chemical classification system (ATC).

4.2 Efficacy Variables

4.2.1 Primary Clinical Efficacy Variable

The first **primary endpoint, a combined endpoint of infection/inflammation, overgrowth, pain and numbness will be evaluated**, as the sum of the following four events:

1. Holgers Index ≥ 2 any time between 3 weeks visit to 1 year at a visit or recorded on the AE page from day 21/3 weeks visit to day 365/1 year visit
2. Any overgrowth (≥ 2) any time between 3 weeks to 1 year
3. Pain (scar/neuropathic) according to POSAS ≥ 3 or pain questions in CRF ≥ 3 any time between 3 weeks to 1 year
4. Any numbness any time between 3 weeks to 1 year

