7.3.8 Numbness

Subjects will be asked if they experience any numbness around the abutment at visit 3-10. The following scale will be used:

1. No numbness
2. Numbness within 2 cm from the abutment
3. Numbness within and beyond 2 cm from the abutment

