7.4 Safety variables

7.4.1 Loss of implant

The loss of implant is defined as the actual loss of the implant from the site of implantation and will be recorded from visit 2 and onwards.

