8.3 Residual risks associated with the investigational device

Clinical outcomes related to the use of Baha implants and abutments have been frequently reported in the scientific literature during the last decades. A literature review¹⁷ was performed in June 2012 in order to assess the current status of Baha implants and surgical products in terms of safety and efficacy. Fifty-five (55) scientific articles met the predefined review criteria. Only one (1) randomised controlled prospective study and one (1) non-randomised prospective study were encountered; the remaining studies were retrospective studies or case reports. One systematic literature review was also included. Ten (10) studies included only paediatric patients, while the remaining studies included

both paediatric and adult patients or adults only. Nineteen (19) of the studies included 100 or more patients.

Overall good outcomes, with acceptable implant survival rates and low incidence of significant adverse reactions, are reported. However, as with any surgical procedure, the use of Baha implants and surgical procedures is not free from complications, which is also reflected in the literature. Reported complications with Baha implants and surgical products are summarised at continuation.

Implant loss is a known complication with Baha implants, and can occur at any time point following implantation. Known reasons for implant loss include: primary failure of osseointegration, loss of osseointegration, trauma, infection leading to implant loss. The literature reports of cumulative implant survival rates in the range 73 to 100%, with the majority of authors reporting survival rates of 90% or higher.

Local skin reactions around the Baha abutment, ranging from slight redness to infected tissue, are the most common complications with Baha implants. Reports suggest that as many as 30% of the patients experience some kind of skin reaction at some point in time. However, the vast majority of skin complications are regarded as minor. Holgers grades of 0-1 are reported in 90-95% of observations, with adverse reactions (grade 2-4) only being reported in a few percent of observations

Excessive skin thickening or skin overgrowing the abutment is another relatively common soft tissue complication. The reported rate of skin thickening/overgrowth ranges between 0 and 22%. In cases where skin thickening recurs following localised treatment and skin revision surgery.

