4.2.3 Secondary Clinical Efficacy Variables

4.2.3.1. The Holgers Index

The **Holgers Index** is designed to capture signs and symptoms of inflammation or infection at the site of implantation. The scale should be completed at visit 3-10.

The following scale will be used:

- | | |
|---|--|
| 0 | No irritation. Epidermal debris removed, if present |
| 1 | Slight redness. Local temporary treatment, if needed |
| 2 | Red and slightly moist tissue. No granulation formation, local treatment and extra controls as indicated |
| 3 | Reddish and moist; sometimes granulations tissue, revision surgery is indicated |
| 4 | Removal of the abutment / implant necessary due to infection |
| R | Removal of implant for reasons not related to skin problems |

Protocol:

Clinical and health economic evaluation with a new Baha abutment design combined with a minimally invasive surgical technique

Protocol No:

CBAS5439

Version:

1.0

Page 12 of
23

Holgers Index will also be categorised into 0-1 vs 2-4 (R) and 0 vs 1-4 (R) at each visit.

Max of Holgers Index per patient during the study will also be analysed.

Holgers Index according to AE reporting will also be analysed. If no stop date for an AE with Holgers Index is entered the AE is ongoing and should be counted from the start date and onwards.

4.2.3.2. *Soft tissue thickening/overgrowth*

In order to capture **soft tissue thickening/overgrowth** the following scale has been developed for this investigation. The scale should be completed at visit 3-10.

The following scale will be used:

- | | |
|---|--|
| 0 | No soft tissue thickening or overgrowth |
| 1 | Slight soft tissue thickening or overgrowth |
| 2 | Moderate soft tissue thickening or overgrowth. Local treatment and extra controls as indicated |
| 3 | Marked/distinct soft tissue thickening or overgrowth. Revision surgery is indicated. |

Max of the soft tissue thickening/overgrowth will be calculated for each patient.

4.2.3.3. *Wound healing*

At visit 3-7 determination if the **wound is healed or not** will be performed.

The **visible abutment length** will be measured at visit 3-10 and change from visit 3 will be calculated.

4.2.3.4. *Aesthetic outcomes*

The **aesthetic outcome** of the surgery will be evaluated by the subject and the surgeon at visit 6, 8 and 10. The scar will be evaluated in accordance with the Patient and Observer Scar Assessment Scale (POSAS) v 2.0 that consists of two parts, a patient scale and an observer scale:

- Patient items:

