5.8 Safety Analyses

5.8.1 *Loss of implant*

The loss of implants will be analysed with the Log-rank test between the two treatment groups and illustrated with Kaplan-Meier survival curves. The survival probabilities at 90 days, 180 days and at 365 days (from the KM-estimates) will be tabulated. Cox proportional Hazard ratio (with 95% CI) of implant loss for treatment group will be presented. Number of loss of implant and total follow up time per treatment group will be presented. Based on these numbers simulations (Markov-Modelling) of different scenarios will be made.

5.8.2 *Adverse Events*

Only treatment-emergent AEs will be included in the summaries for safety population.

A summary of subjects reporting at least one of the following AEs will be presented in an overview table:

- Any AE
- Any SAE
- Any treatment-related AE (Probably + Definitely)
- Any treatment-related SAE (Probably + Definitely)
- Death

Summaries per System Organ Class (SOC) and Preferred Term (PT) presenting n of AEs and n (%) of subjects with at least one AE will be provided for:

- All AEs (includes all serious and non-serious AEs)
- All AEs by Severity
- All AEs by Relation to Treatment
- All SAEs

5.8.3 *Device deficiency*

Number of Device Deficiencies and number and percentage of patients with a Device Deficiency.

5.8.4 *Removal of abutment*

Number and percentage of removal of abutment will be presented by treatment group.

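### The primary sum has no rule for implant loss or Holgers grade R, so an early non-infectious loss can score 0, and no planned analysis of the combined variable counts loss as an event

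*SAP*

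**What the plan says.** SAP 4.2.1 builds the first primary endpoint "as the sum of the following four events". Item 1 is "Holgers Index ≥ 2 any time between 3 weeks visit to 1 year at a visit or recorded on the AE page", with the AE-page window running from day 21 to day 365. The other items are overgrowth of grade 2 or more, pain of 3 or more, and any numbness. Neither implant loss nor grade R is mentioned.

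Grade R is on the Holgers scale, as "Removal of implant for reasons not related to skin problems". Protocol 7.3.1 marks it, like grades 2 to 4, for reporting on the AE page. For the secondary variable, SAP 4.2.3.1 states: "Holgers Index will also be categorised into 0-1 vs 2-4 (R) and 0 vs 1-4 (R) at each visit".

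Loss is handled separately as a safety variable. Protocol 7.4.1: "The loss of implant is defined as the actual loss of the implant from the site of implantation". SAP 5.8: "The loss of implants will be analysed with the Log-rank test between the two treatment groups", with Kaplan-Meier estimates at 90, 180 and 365 days, a Cox hazard ratio and a table of abutment removals by arm. The combined variable is repeated on the PP population and on subjects who completed all visits (SAP 5.7.2). SAP 5.1 promises unspecified sensitivity analyses if much data is missing.

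For HUI-III and APHAB, SAP 4.2.5.6 does say what value to use after extrusion or removal.

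**The concern.** Holgers and overgrowth describe tissue at an abutment, and numbness is asked about in relation to it: "Subjects will be asked if they experience any numbness around the abutment at visit 3-10". Once the implant is gone, later Holgers and overgrowth events cannot normally arise. Such a subject stays in the ITT population, because one measurement from day 10 onward is enough (SAP 3.1.1). With no earlier event, the recorded score can be 0, the same as an uneventful year.

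This is not ordinary missing data. The outcome is known and unfavourable, and it truncates the primary score. If losses differ between arms, the arm with more of them can look slightly better on the primary endpoint. The silence on grade R adds a coding problem: two programmers following SAP 4.2.1 could give the same removed implant 0 or 1.

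**Working it through.** **Inputs.** Protocol 9.2.1 and SAP 2.4.1: 50 evaluable per arm; two-sided Mantel-Haenszel chi-square at 0.0499; distribution of 0 to 4 events of 60/18/12/7/3% in control and 81/13/5/1/0% in test.

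Mean, control: 0.18 + 2(0.12) + 3(0.07) + 4(0.03) = 0.75. Mean, test: 0.13 + 2(0.05) + 3(0.01) = 0.26. Difference: 0.49.

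**Reproducing the plan's figure.** The statistic is (N − 1)r², where r is the correlation of arm with score. It is compared with 1.9608² = 3.845. With at least 100,000 simulated trials per scenario, power at 50 per arm is 80.6%, against the stated 80%.

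**Possible loss rates.** The documents give none by arm, by cause or at 1 year.
- Protocol 8.3 (literature): cumulative survival of 73 to 100%, "with the majority of authors reporting survival rates of 90% or higher". A 10% loss is 0.10 × 50 = 5 per arm; 27% is 13.5 per arm.
- Protocol 8.2 (complaint reports against units sold, BA300 products): 21/11,600 = 0.18% and 4/1,800 = 0.22%, about 0.1 per arm.

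The first range pools study types, including paediatric series. The second may under-report.

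**Assumed scenarios.** A fixed number of subjects is lost and the rest follow the planning distributions. Entries are power for a result favouring test.

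| Losses (test / control) | Scored 0 | Excluded | Scored 1 | Scored 4 |
|---|---|---|---|---|
| 3 / 1 | 82% | 79% | 74% | 23% |
| 2 / 0 | 83% | 79% | 75% | 34% |
| 2 / 2 | 78% | 79% | 78% | 57% |

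**Mean difference, 3 / 1.** With each loss scored s, it is (49 × 0.75 + s)/50 − (47 × 0.26 + 3s)/50.
- s = 0: 0.735 − 0.244 = 0.49
- s = 1: 0.755 − 0.304 = 0.45
- s = 4: 0.815 − 0.484 = 0.33

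**Separating bias from variance.** With 2 / 2 losses the mean difference is 48 × 0.49/50 = 0.47 whatever s is, yet power falls from 78% (s = 0) to 57% (s = 4). That fall is added variance alone. Part of the 23% in the 3 / 1 row has the same cause.

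**No true difference.** With the control distribution in both arms, the chance of a significant result favouring test is 2.4% without losses. It is 3.3% with 3 / 1 losses scored 0. With losses in the test arm only, scored 0, it is 3.6% at a 5% loss rate, 5.1% at 10% and 15.7% at 27%.

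**The case against.** The strongest reply is that the scale already has a grade for this situation. R is AE-reportable, item 1 accepts AE-page entries, and SAP 4.2.3.1 puts R with the adverse grades. If that grouping carries over, a removal coded R scores 1. This stands as far as it goes, and it rules out saying flatly that loss contributes no event. But SAP 4.2.1 does not adopt the grouping. R is worded as a removal, so whether a spontaneous loss is graded R is open. An R entered before day 21 would also fall outside item 1's window.

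A reader might also infer that a lost implant automatically scores as the best result. It does not: events before the loss count, and pain and numbness can still be recorded afterwards. Removal for pain would normally have scored under item 3 already. A score of 0 is possible, not certain.

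Nor is it right that nothing in the plan would show the problem. Loss is compared by arm, abutment removals are tabulated, and component values are plotted by patient over time (SAP 5.7.1.1). What is missing is narrower. The PP and completer repeats may drop these subjects rather than count them, and the log-rank test does not show whether the combined result survives counting them.

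Finally, the 23% should not be read as the size of the distortion. It reflects a choice to treat one loss as all four events at once, a category planned at 3% in control and 0% in test. Scoring 0 rather than excluding moves power by about 3 points in the 3 / 1 case. Both arms use the same 4 mm implant, and no document supports that particular split.

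**Conclusion.** The concern holds as a gap in the definition and in the sensitivity analyses. The primary sum omits implant loss, leaves grade R unresolved and has no rule for visits after loss, whereas the SAP does have such a rule for HUI-III and APHAB. An early non-infectious loss with no earlier event can score 0, and no planned analysis of the combined variable counts it as an event.

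The size depends on loss rates that the documents do not give. At the complaint-report rate of about 0.2% the effect is negligible. With 3 versus 1 losses out of 50 per arm, power favouring test ranges from 82% (scored 0) through 79% (excluded) and 74% (one event) to 23% (scored 4), the last partly from variance. These figures assume the plan's event distributions for all other subjects and no event in those lost. The documents do not support a claim that the primary result will be biased in favour of test, only that the plan could not show otherwise.

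**What to change.** In SAP 4.2.1, count Holgers R under item 1, consistent with the grouping in SAP 4.2.3.1, and say whether spontaneous loss is to be graded R.

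In SAP 5.7.1.1, add a pre-specified ITT sensitivity analysis of the combined variable in which any implant loss or removal, or permanent abutment removal, before the 1-year visit counts as at least one event. Repeat it with those subjects in the worst category (4) as an extreme bound. Report the number re-scored in each arm.

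Interpret the primary result alongside these analyses and the between-arm comparison of loss. Do not attach an automatic rule that downgrades the claim: the 2 / 2 scenario shows that scoring 4 lowers power substantially even when losses are equal.

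The test and the 0.0499 level stay as they are, and the data are already collected. The cost is one extra table and a supportive result that may be less favourable.

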5.2 Variables

5.2.1 Primary efficacy variables

The first primary endpoint, a combined endpoint of infection/inflammation, overgrowth, pain and numbness will be evaluated, as the sum of the following four events:

1. Holgers Index ≥ 2 any time between 3 weeks to 1 year
2. Any overgrowth any time between 3 weeks to 1 year
3. Pain (scar/neuropathic) according to POSAS ≥ 3 any time between 3 weeks to 1 year
4. Any numbness any time between 3 weeks to 1 year

The second primary endpoint: direct medical cost associated with the surgery (time to perform surgery, number of wound dressings sessions and cost to treat complications) will be calculated for each subject using standard cost/unit in each participating country.

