5.2.2 Secondary efficacy variables

The secondary efficacy variables will be evaluated as follows:

- Infections/inflammations will be evaluated by the Holgers Index
- Soft Thickening/overgrowth scale (0-2)
- Wound healing will be evaluated by the surgeon/surgical nurse.
- Numbness (paraesthesia) – the patients will indicate if they experience numbness and the area where they have the problem on a scale from 0-2.
- Pain in the scar area and neuropathic pain will be evaluated by the patient using ‘The Patient and Observer Scar Assessment Scale (POSAS)’ (1-10)
- Aesthetics will be evaluated by the subject and the surgeon using ‘The Patient and Observer Scar Assessment Scale (POSAS)’(two scales):
 - Patient aesthetic scale (1-10)
 - Observer aesthetic scale (1-10)
- Surgery time (min)

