7.3.2 Soft tissue thickening/overgrowth scale

In order to capture soft tissue thickening/overgrowth the following scale has been developed for this investigation. The scale should be completed at visit 3-10.

The following scale will be used:

- 0 No soft tissue thickening or overgrowth
- 1 Slight soft tissue thickening or overgrowth
- 2 Moderate soft tissue thickening or overgrowth. Local treatment and extra controls as

indicated*

3 Marked/distinct soft tissue thickening or overgrowth. Revision surgery is indicated.*

* Should also be reported on the AE page in the CRF

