9.2 Sample size calculation

Sample size calculations are performed for both primary analyses. The significance level of 0.05 will be split between the two primary analyses: combined endpoint 0.0499 and direct medical cost 0.0001.

9.2.1 Sample size calculation for the combined endpoint of infection/inflammation, overgrowth, pain and numbness

For a definition of first primary endpoint, see section 5.2.1. It is estimated that the distribution of the number of events regarding infection/inflammation, overgrowth, pain and numbness with the traditional surgical procedure and BA300 abutment is as follows; 60% no events, 18% one event, 12% two events, 7% three events and 3% four events. In order to achieve a power of 80% with the Mantel-Haenszel two-sided chi-square test at significance level of 0.0499 when the distribution of the number of events with the new surgical procedure and new abutment BA400 is as follows; 81% no events, 13% one event, 5% two events, 1% three events and 0% four events we need 50 statistical evaluable subjects in each group. The sample size calculation is based on 10000 simulated studies.

9.2.2 Sample size calculation for direct medical costs, based on time for surgical procedures, wound healing and complications

For a definition of the second primary endpoint see section 5.2.1. The power that is achieved if the previously needed 50 statistical subjects in each group are used for the economic evaluation is calculated as follows, From a 12 months prospective follow-up by Hultcrantz² the mean time required for surgery was 44.57 (SD 7.41) minutes with skin reduction and 28.14 (SD 3.67) minutes without skin reduction. If a normal distribution of the costs time required for surgery, 15% infections/inflammations, 15% extra dressings with skin reduction, 9% infections/inflammations and 10% extra dressings without skin reduction, with a power of more than 99% with the two-sided Mann-Whitney U-test at a significance level 0.0001 would be achieved. The sample size calculation is based on 10000 simulated studies.

In order to compensate for a drop-out rate of 5% we need to randomize 53 subjects to each group

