5.7.2 Secondary Efficacy Analyses

The combined variable used in the primary analysis will also be analysed in the same way but for PP population and also only for subjects who completed all visits in the study.

The distribution of Holgers Index will be tested between treatment groups with Mantel-Haenszel Chi-square test at each visit. Holgers index by visit will also be presented in a figure. Max of Holgers Index per patient will be tested in the same way but only once and not per visit. The distribution of all Holgers Index values over all visits will be presented but no testing of this will be done.

Holgers Index according to AE reporting will be analysed by:

- Plot the incidence rate Holgers ≥ 2 per day over time
- Plot individual patient Holgers Index values using boxes/bars indicated by different colours by severity with patients on y-axis and calendar time on x-axis.
- The distribution of all Holgers Index values over all AEs will be presented by treatment group but no testing of this will be done.
- Plot visit Holgers data and movement between visits by treatment group.

The distribution of soft tissue thickening/overgrowth will be tested between treatment groups with Mantel-Haenszel Chi-square test at each visit.

The number of resources and costs of the components Direct medical costs will be summarised by treatment groups. The costs of the 3 components: surgery, wound dressing and complications will be tested between groups by using Mann-Whitney U test.

Wound healing will be tested between treatment groups by visit with Fishers exact test.

The visible abutment length and change from visit 3 will be tested between groups by visit by using Mann-Whitney U test. This test will only be done for patients with no change of abutment. For patients with an abutment change spaghetti plots will be created of the visual abutment length over time with indication of when abutment change is made and an indication of length of the new abutment.

The aesthetic outcome (POSAS) scales and the two pain questions will be tested between groups by visit by using Mann-Whitney U test.

The distribution of numbness will be tested between treatment groups with Mantel-Haenszel Chi-square test at each visit.

Surgery time will be tested between groups by using Mann-Whitney U test.

STATISTISKA KONSULTGRUPPEN		Statistical Analysis Plan	

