7 CHANGES OF ANALYSIS FROM PROTOCOL

The primary economical variable is defined as the following in the protocol:

Protocol:

Clinical and health economic evaluation with a new Baha abutment design combined with a minimally invasive surgical technique

Protocol No:

CBAS5439

Version:

1.0

Page 21 of 23

“direct medical cost associated with the surgery (time to perform surgery, number of wound dressings sessions and cost to treat complications)”

It is now changed to be able to include more costs and is now defined as:

“direct medical cost associated with the surgery (all health care costs, incurred, related to the procedure)”

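### The SAP counts overgrowth in the first primary endpoint only from grade 2, the protocol counts any overgrowth, and the change is neither declared nor covered by a sensitivity analysis

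*SAP*

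**What the plan says.** Protocol 5.2.1 defines the overgrowth component as "Any overgrowth any time between 3 weeks to 1 year". SAP 4.2.1 defines it as "Any overgrowth (≥ 2) any time between 3 weeks to 1 year".

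The scale is the same in Protocol 7.3.2 and SAP 4.2.3.2. Grade 0 is "No soft tissue thickening or overgrowth", grade 1 is "Slight soft tissue thickening or overgrowth", grade 2 is moderate and grade 3 is marked.

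Protocol 9.2.1 ties the sample size to the protocol rule: "For a definition of first primary endpoint, see section 5.2.1". SAP 2.4.1 repeats the same event distributions and the same 50 evaluable subjects per group.

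SAP section 7 records one change from the protocol, to the cost endpoint: "It is now changed to be able to include more costs and is now defined as" a wider set of health care costs. It does not mention overgrowth. SAP 5.7.2 adds two further analyses of the composite, one per protocol and one in subjects who completed all visits: "The combined variable used in the primary analysis will also be analysed in the same way but for PP population". Both therefore inherit the grade 2 cut-off.

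**The concern.** The SAP line contradicts the protocol and also its own scale, because on a scale that starts at 0 for none, grade 2 or more is not *any*. In the same list the protocol gives numeric cut-offs where it wants them (Holgers 2 or more, POSAS pain 3 or more) and writes *any* for overgrowth and numbness, so the plain reading is everything above grade 0.

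The composite takes 0.0499 of the 0.05 alpha. If the rules differ, the same data can be significant under one document and not under the other, and a reader cannot tell which result is confirmatory. The trial is open, and Protocol 9.10 requires the SAP to be signed only before database lock. The documents do not show that anyone saw data before the cut-off changed. They also give no reason or date for it, which an entry in section 7 would supply.

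**Working it through.** **1. How one subject is scored**

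| Worst overgrowth grade, 3 weeks to 1 year | Protocol 5.2.1 | SAP 4.2.1 |
|---|---|---|
| 0 | 0 | 0 |
| 1 | 1 | 0 |
| 2 or 3 | 1 | 1 |

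The discrepancy rests on this table alone. The calculation below only indicates its possible size.

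**2. The plan's own power figure** (inputs from Protocol 9.2.1)

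- Control, 0 to 4 events: 60/18/12/7/3%. Mean = 0.18 + 2(0.12) + 3(0.07) + 4(0.03) = 0.75.
- Test, 0 to 4 events: 81/13/5/1/0%. Mean = 0.13 + 2(0.05) + 3(0.01) = 0.26.
- Difference 0.49; n = 50 per group; two-sided alpha 0.0499.
- Test statistic: Mantel-Haenszel chi-square, (N - 1)r² with N = 100 and scores 0-4, on 1 degree of freedom.

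Simulation with 200,000 trials gives 80.6% power, so the stated 80% is reproduced. As a cross-check, the variances are 1.77 - 0.75² = 1.2075 and 0.42 - 0.26² = 0.3524, which gives an average SD of √0.77995 = 0.883. Then 0.49/(0.883 × √(2/50)) = 2.77, and 2.77 - 1.96 = 0.81, or about 79% power.

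**3. Illustration of the SAP rule**

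Three assumptions are not in the documents:

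- The planned distributions describe the protocol rule.
- The four components are exchangeable, so a subject with k events has overgrowth among them with probability k/4.
- A stated share of overgrowth events never exceeds grade 1 and is lost under the SAP rule.

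The implied overgrowth rates are 0.75/4 = 18.75% in control and 0.26/4 = 6.5% in test, or 9.4 and 3.25 subjects per 50. With the same share g in both arms, the mean difference becomes 0.49(1 - g/4). Both rules were applied to the same simulated trials, 200,000 per scenario.

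| Grade-1 share, control / test | Subjects per 50 losing an event, control / test | Mean difference | Power, SAP rule | Significant under protocol rule only | Significant under SAP rule only |
|---|---|---|---|---|---|
| 25% / 25% | 2.3 / 0.8 | 0.459 | 79.1% | 3.1% | 1.5% |
| 50% / 50% | 4.7 / 1.6 | 0.429 | 77.6% | 4.9% | 1.8% |
| 75% / 75% | 7.0 / 2.4 | 0.398 | 76.1% | 6.5% | 2.1% |
| 75% / 25% | 7.0 / 0.8 | 0.366 | 65.8% | 15.0% | 0.2% |
| 25% / 75% | 2.3 / 2.4 | 0.492 | 86.5% | 0.6% | 6.7% |

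Adding the last two columns, the rules disagree in 4.6%, 6.7% and 8.6% of trials with equal shares, and in 15.2% and 7.3% with unequal shares.

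**4. Sensitivity to exchangeability**

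With overgrowth weighted at half or double the other components (100,000 trials each), equal shares give 75-80% power. The two unequal cases give 59-71% and 84-89%.

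**The case against.** The best counter-argument is that the SAP only clarifies. The protocol gives no numeric cut-off here. Its scale merges thickening with overgrowth while the endpoint names only overgrowth, so grade 1 could be slight thickening alone. Grades 2 and 3 are those that also go on the adverse event page, as Holgers 2 and above do, and Holgers 2 is the cut-off for the first component. Protocol 9.10 leaves detail to the SAP. This reading is possible, but the SAP does not state it and the word *any* was kept. If grade 2 was intended, it is still a change to the primary endpoint that has to be listed.

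A second objection is that the information is not lost. The SAP tests overgrowth by visit on the full scale, derives each patient's maximum grade, and plots individual component values from 3 weeks to 1 year. A reader could largely rebuild the protocol-rule composite from these. That stands, but none of them is a prespecified test of the four-event sum.

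Third, the magnitude depends on assumptions. The grade-1 share is invented, the documents give no component rates, and exchangeability is doubtful. In the 14-patient comparison cited in Protocol 1.1.2, numbness at 12 months was 6 of 7 against 1 of 7, and reweighting overgrowth alone does not test a composite dominated by numbness. The implied 18.75% control rate lies near the top of the 0-22% range in Protocol 8.3. Nothing in the documents supports sharply unequal shares. All of this stands, so the figures are illustrative and the point does not depend on them.

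**Conclusion.** The point holds and should be fixed before the composite is analysed. The two documents define one component of the main primary endpoint differently, the SAP does not declare the difference, and no planned analysis gives the composite under the protocol rule. This follows from the text alone.

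The effect on the result cannot be determined from the documents. Under the stated assumptions the loss of power is modest when grade-1 shares are equal, up to about 5 percentage points (80.6% to 76.1%). Unequal shares could shift it in either direction. The documents do not show why the cut-off changed or which arm it favours.

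**What to change.** Use one cut-off, stated by grade, in both documents.

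- **Default:** in SAP 4.2.1 item 2, count overgrowth of grade 1 or more, as Protocol 5.2.1 implies, and report the composite at grade 2 or more as a named sensitivity analysis.
- **If grade 2 or more is intended:** delete *any*; list the change in SAP section 7 with its reason and its timing relative to data access; and prespecify the composite under the protocol rule as a sensitivity analysis.

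As a minor related correction, Protocol 5.2.2 gives the scale range as 0-2 while Protocol 7.3.2 and SAP 4.2.3.2 use 0-3. Reconcile these at the same time.

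The cost is a change of wording, one entry in section 7 if grade 2 is kept, and one extra table. Grades are already collected at visits 3 to 10, so no new data are needed, and the sample size is unchanged under the default.
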